NCI	National Cancer Institute
NHL	Non-Hodgkin Lymphoma
ORR	Overall Response Rate
OS	Overall Survival
PBMCs	Peripheral Blood Mononuclear Cells
PD	Progressive Disease
PFS	Progression Free Survival
p.o.	per os/by mouth/orally
PR	Partial Response
PRR	Partial Response Rate
RP2D	Recommended phase II dose
QOD	Every other day
SAE	Serious Adverse Event
SD	Stable Disease
SGOT	Serum Glutamic Oxaloacetic Transaminase
SPGT	Serum Glutamic Pyruvic Transaminase
WBC	White Blood Cells

STUDY SCHEMA

- DLT period (Phase I only): 21 days of induction
- Duration of treatment (Phase I and II): one year, or until POD (whichever occurs first)
- Primary objective assessment: toxicity after week 4 treatment (Phase I only); scans after induction treatment and/or after consolidation treatment (if applicable) (Phase II only)

*This may be repeated once at discretion of treating investigator; see Section 4.0 (TREATMENT PLAN) for details.

DOSING SCHEMA (in weeks, continued for one year total, or until POD)

STUDY SUMMARY

Title	A Phase I-II Trial of Brentuximab Vedotin Plus Rituximab as Frontline Therapy for Patients with Lymphomas of Immunosuppressed States
Version Date	June 14, 2017 (Amendment 8)
Protocol Number	NU 12H09
Phase	I/II
Methodology	Open-label, single-arm
Study Duration	Approximately 30 months
Study Center(s)	Northwestern University, University of Chicago
Objectives	
Primary objectives: Phase I: Evaluate the safety of brentuximab vedotin and rituximab in patients with immunosuppressed lymphoid malignancies and to determine the recommended phase II dose (RP2D) of the combination. Phase II: Evaluate the efficacy of brentuximab vedotin and rituximab in patients with immunosuppressed lymphoid malignancies.
 
Secondary objectives: Phase II:
 
 1. Further evaluate the frequency and severity of toxicity. 2. Further evaluate the efficacy as measured by one-year PFS and OS. 3. Determine the effects of the combination of brentuximab vedotin and rituximab on markers of EBV activation and proliferation. 4. Further evaluate efficacy as measured by time to initiation of cytotoxic chemotherapy. 5. Further evaluate efficacy as measured by observed rates of graft rejection. 
Exploratory objectives (Phase I and II): Correlate response and outcomes with CD30 expression and EBV markers and levels.

Number of Subjects	Phase I: 3-9 patients; Phase II: 24 patients
Diagnosis and Main Inclusion Criteria	Adult patients with non-Hodgkin's lymphoma (NHL) related to an immunosuppressed state
Study Product(s), Dose, Route, Regimen	Brentuximab vedotin 1.2 mg/kg IV once weekly for 3 weeks, then 1.8 mg/kg IV once every 3 weeks Rituximab 375 mg/m ² IV once weekly x 4, then once every 6 weeks
Duration of administration	1 year

Statistical Methodology	
Our null hypothesis is that the combination of rituximab and brentuximab vedotin will yield no difference in the ORR as compared to that observed with historical treatments. The historical ORR for both PTLD and EBV-related lymphoma of the elderly, when treated with rituximab (with or without chemotherapy) is estimated at approximately 50% [1, 2]. Therefore, the optimal two-stage design to test the null hypothesis that $P = 0.50$ versus the alternative that $P \geq 0.70$ (the hypothesized ORR to rituximab plus brentuximab vedotin) has an expected sample size of 24. Under these conditions, if the combination is actually not significantly more efficacious, there is a < 0.05 probability (also known as the alpha value) of concluding that it is. If the combination is actually significantly more efficacious, there is a < 0.20 probability (also known as the beta value) of concluding that it is not. Early futility may be declared, such that if 8 or fewer responses are observed among the first 15 patients enrolled, the trial will be stopped and considered no more efficacious than therapy with rituximab alone.

--------------------------------	---

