10.1.2 Phase II

Our null hypothesis is that the combination of rituximab and brentuximab vedotin will yield no difference in the rate of ORR as compared to that observed with historical treatments. The historical ORR for both PTLD and EBV-related

lymphoma of the elderly, when treated with rituximab (with or without chemotherapy is estimated at approximately 50% [1, 2]. Therefore, the optimal two-stage design to test the null hypothesis that $P=0.50$ versus the alternative that $P>=0.70$ (the hypothesized ORR to rituximab plus brentuximab vedotin) has an expected sample size of 24. Under these conditions, if the combination is actually not significantly more efficacious, there is a <0.05 probability (also known as the alpha value) of concluding that it is. If the combination is actually significantly more efficacious, there is a <0.20 probability (also known as the beta value) of concluding that it is not. Early futility may be declared, such that if eight or fewer responses are observed among the first 15 patients enrolled, the trial will be stopped and considered no more efficacious than therapy with rituximab alone.

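### A Phase II stop at 8 or fewer of 15 responses supports not continuing, but not the attached conclusion that the combination adds nothing to rituximab

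*Combined protocol and SAP*

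**What the plan says.** The Statistical Methodology entry of the Study Summary and section 10.1.2 describe an optimal two-stage test of a 50% overall response rate (ORR) against 70% or more. The design "the hypothesized ORR to rituximab plus brentuximab vedotin) has an expected sample size of 24". Two error statements follow. If the combination is not better, "there is a <0.05 probability (also known as the alpha value) of concluding that it is"; if it is better, "there is a <0.20 probability (also known as the beta value) of concluding that it is not".

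Both places then allow early futility to be declared: "if 8 or fewer responses are observed among the first 15 patients enrolled" (Study Summary; section 10.1.2 spells out the number), "the trial will be stopped and considered no more efficacious than therapy with rituximab alone".

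The study is "Open-label, single-arm". The benchmark is the historical ORR, which "when treated with rituximab (with or without chemotherapy) is estimated at approximately 50" per cent. The null hypothesis is framed against historical treatments in general, not against rituximab monotherapy.

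Section 7.5 (Stopping Rules) also covers a first-stage stop. Its boundary is four or fewer complete or partial responses among the first 15 patients treated, and it labels that result inadequate efficacy.

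**The concern.** A futility look answers one question: is it worth enrolling more patients? The wording goes further and states what a stop means for efficacy. Failing to clear a hurdle set with a 70% target in mind does not show that the regimen is no better than 50%, and at the boundary itself the observed rate is higher than the benchmark.

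Two things are at stake. A report that follows the plan literally would carry a negative comparative conclusion that the triggering data may not support. It would also name a comparator, rituximab alone, that the trial does not contain and that the benchmark does not isolate.

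**Working it through.** **Inputs.** Null p0 = 0.50, alternative p1 = 0.70, alpha below 0.05, beta below 0.20, first-stage boundary 8/15 and expected sample size 24, all from the Study Summary and section 10.1.2. The competing boundary of 4/15 is from section 7.5.

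**1. Reproduce the plan's figure.** An exact binomial search over two-stage designs, with one-sided alpha at most 0.05 and power at least 0.80, gives as optimal: stop at 8/15 or fewer; otherwise continue to 43 patients and declare activity with more than 26 responses. Its alpha is 0.0499 and its power 0.8044. The probability of stopping early at p0 is 0.6964, so the expected sample size is

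15 + (1 − 0.6964) × (43 − 15) = 15 + 0.3036 × 28 = 23.5,

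which rounds to the stated 24. The 8/15 boundary is therefore the correct first stage of the design described.

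**2. How often the stop occurs.** P(X ≤ 8) = Σ C(15,k) p^k (1 − p)^(15 − k), for k = 0 to 8:

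| True ORR | P(8 or fewer of 15) |
|---|---|
| 50% | 0.696 |
| 55% | 0.548 |
| 60% | 0.390 |
| 65% | 0.245 |
| 70% | 0.131 |

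**3. What the data can say when the stop occurs.** Exact (Clopper-Pearson) 95% limits are the 0.025 quantile of Beta(x, 16 − x) and the 0.975 quantile of Beta(x + 1, 15 − x):

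| Responses | Observed ORR | Exact 95% CI |
|---|---|---|
| 8/15 | 53.3% | 26.6% to 78.7% |
| 7/15 | 46.7% | 21.3% to 73.4% |
| 6/15 | 40.0% | 16.3% to 67.7% |
| 5/15 | 33.3% | 11.8% to 61.6% |
| 4/15 | 26.7% | 7.8% to 55.1% |
| 3/15 | 20.0% | 4.3% to 48.1% |

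At 7 or 8 responses the interval still contains the 70% target. From 4 to 8 the upper limit is above 50%. Only at 3 or fewer does it fall below 50%.

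If every continuing outcome is ranked above every stopped one, these single-stage limits also hold for a first-stage stop in the two-stage design.

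**4. How much of the stopping region this covers.** At a true ORR of exactly 50%, P(X ≤ 3) = 1 − 0.9824 = 0.0176. The share of stops with 4 to 8 responses is (0.6964 − 0.0176) / 0.6964 = 0.975.

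**5. Set against the disclosed beta.** At 70% the total miss probability of the 43-patient design is 1 − 0.8044 = 0.196. Of this, 0.131 comes from the first stage and 0.196 − 0.131 = 0.065 from the second.

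**6. The section 7.5 boundary.** P(X ≤ 4) is 0.059 at a true ORR of 50% and 0.0007 at 70%. A first-stage stop under 7.5 is thus a much rarer event than under 10.1.2.

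**The case against.** The best defence is that the phrase is only the decision label of a two-stage test. The sentence opens by saying that futility may be declared, the null is no difference from the historical rate, and no equivalence analysis is planned. The sentence before it discloses a chance below 0.20 of missing a better regimen. The probabilities at 55% to 65% lie between null and alternative, where the plan claims no power; the full 43-patient design would itself miss a true 60% with probability 1 − 0.3491 = 0.65.

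Much of this stands, and it rules out several stronger readings:

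- A reader might infer that the stop carries a hidden or excessive error rate. At the plan's own alternative it does not: 0.131 is inside the stated beta.
- A reader might infer that 15 patients can never support the conclusion. Against the 50% figure they can, at 3 or fewer responses.
- A reader might infer that this is the plan's only statement of what a first-stage stop means. Section 7.5 gives another, in more measured terms.
- A reader might want formal cutoffs after the stop, such as requiring an upper limit below 50% before saying no better. Those are not part of the design, and a regimen at exactly 50% would meet that one with probability only 0.018.

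What the defence does not answer is the wording. Not rejecting a null is not showing that it holds, and beta tied to 70% does not license a statement about any improvement over 50%. Nor does it supply a rituximab-alone comparison.

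**Conclusion.** The concern holds as a point about the stated conclusion, not about the boundary. A stop at 8 or fewer of 15 justifies not continuing. For 4 to 8 responses it does not justify saying that the combination is no better than 50%, and at no count does a single-arm trial with this mixed benchmark isolate rituximab alone. If the true ORR were 60%, the unsupported label would be triggered about 39% of the time; at 70%, about 13%.

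The stopping probabilities and intervals assume independent patients, all 15 counted in the denominator, and 8/15 as the governing boundary. The 0.196 also assumes the 26/43 second stage, which the plan does not state. Severity is minor: the observed count can be reported either way, and the number of patients enrolled does not depend on this phrase.

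**What to change.** In the Study Summary and section 10.1.2, replace the words that follow the statement that the trial will be stopped with:

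*for insufficient evidence of activity relative to the 50% historical rate to justify continuing; the ORR will be reported with its exact 95% CI.*

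Add no further cutoffs after the stop. In the same amendment, reconcile this text with section 7.5 so that all three places give one first-stage boundary, one definition of the first 15 patients (enrolled or treated) and one conclusion. The 8/15 boundary is the one that reproduces the stated expected sample size.

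The cost is a slightly less definitive negative statement and one extra confidence interval. The rewording changes neither the 8/15 boundary nor the enrolment and error rates that go with it.

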1.0 BACKGROUND AND RATIONALE

1.1 Disease Background

It is estimated that in 2010, there were 65,540 cases of NHL in the United States, and 20,210 deaths from the disease [3]. Diffuse Large B-Cell Lymphoma (DLBCL) is the most common sub-type of NHL, with approximately 20,000 new cases in the United States each year [3]. Chemo-immunotherapy consisting of rituximab, cyclophosphamide, doxorubicin, vincristine, and prednisone (R-CHOP) remains the standard first-line treatment, and autologous stem cell transplant (ASCT) is generally the preferred second-line treatment [4]. However, there remain many patients for whom ASCT is not an option, or who relapse in spite of this therapy, and approximately one-third of all patients with DLBCL will die due to disease relapse [5]. Therefore, additional treatment options are urgently needed.

Chronic immunosuppression significantly increases the risk for a variety of lymphoid malignancies, which together are termed post-transplant lymphoproliferative disorder (PTLD) [6]. These immunosuppressed patients face a roughly six-fold lifetime risk of lymphoma as their immunocompetent counterparts [7]. Although DLBCL is the most common histology, other NHL, as well as Hodgkin's Lymphoma (HL) and Peripheral T-Cell Lymphoma (PTCL) have all been reported as PTLD variants. Up to 86% of PTLD cases are EBV-associated [8]; roughly 70% express CD30 [9]; and over 80% of PTLD express CD20 [10]. Although the PTLD population is a heterogeneous one, outcomes are generally poor, with recent larger studies reporting median overall survival (OS) in the range of 2-4 years [11, 12]. Rates of treatment-related mortality (TRM) of 13-50% are moreover striking when these patients are treated with early cytotoxic chemotherapy [13-15], and significant rates of graft rejection have also been reported in this context.

EBV-related lymphoma of the elderly is likewise a variant of aggressive B-cell lymphoma [16], and represents up to 10% of cases of DLBCL in adults [17]. In a vein similar to PTLD, immuno-senescence (of the elderly) is thought to put patients at risk for these tumors, which generally co-express CD20 and CD30. Prognosis is generally poor, including when treated with cytotoxic chemotherapy [18]. Therefore, better and more tolerable treatment strategies are needed for PTLD and EBV-related lymphoma of the elderly.

Finally, autoimmune disorders, such as systemic lupus erythematosus (SLE), rheumatoid arthritis (RA), and Sjogren's syndrome (SS) are associated with increased risk of development of NHL, whether related to underlying disruption of normal lymphocyte function [19], or to pharmacologic immunosuppression with cytotoxic agents or TNF α inhibitors [20]. Interestingly, studies suggest that about 60% of such cases are indolent lymphomas [19, 21], suggesting that anthracycline-based therapy may be unnecessarily toxic. No standard of therapy exists for such types of lymphoma, and treatment is generally guided by histologic subtype and the clinical status of the patient.

1.2 Study Agent(s) Background and Associated Known Toxicities

1.2.1 Brentuximab vedotin

1.2.1.1 Toxicity Summary

Because clinical trials are conducted under widely varying conditions, adverse reaction rates observed in clinical trials of a drug cannot be directly compared to rates in the clinical trials of another drug and may not reflect the rates observed in practice. Brentuximab vedotin was studied as monotherapy in 160 patients in two phase 2 trials. Across both trials, the most common adverse reactions ($\geq 20\%$), regardless of causality, were neutropenia, peripheral sensory neuropathy, fatigue,

nausea, anemia, upper respiratory tract infection, diarrhea, pyrexia, rash, thrombocytopenia, cough and vomiting.

Brentuximab vedotin was studied in 102 patients with HL in a single arm clinical trial in which the recommended starting dose and schedule was 1.8 mg/kg intravenously every 3 weeks. Median duration of treatment was 27 weeks (range, 3 to 56 weeks). The most common adverse reactions ($\geq 20\%$), regardless of causality, were neutropenia, peripheral sensory neuropathy, fatigue, upper respiratory tract infection, nausea, diarrhea, anemia, pyrexia, thrombocytopenia, rash, abdominal pain, cough, and vomiting.

Brentuximab vedotin was studied in 58 patients with sALCL in a single arm clinical trial in which the recommended starting dose and schedule was 1.8 mg/kg intravenously every 3 weeks. Median duration of treatment was 24 weeks (range, 3 to 56 weeks). The most common adverse reactions ($\geq 20\%$), regardless of causality, were neutropenia, anemia, peripheral sensory neuropathy, fatigue, nausea, pyrexia, rash, diarrhea, and pain. Following IV administration of 1.2 mg/kg brentuximab vedotin, both patients with hepatic impairment (Child-Pugh class A-C) and patients with severe renal impairment (CrCl < 30 mL/min) exhibited a trend toward moderate decreases in ADC exposure and increases in MMAE exposure.

In addition, there is an ongoing contemporaneous phase II clinical trial using consecutive doses (q 3 weeks 1.8mg/kg) of 'single-agent' SGN-35 for elderly Hodgkin lymphoma patients. As of May 1st 2013, 11 out of 30 planned patients have been enrolled. Ten of the 11 patients have received at least 2 cycles of SGN-35, while 4 patients have received at least 6 SGN-35 cycles. Among these patients, there have been 2 SAEs identified (grade 3 orthostatic hypotension and weakness in patient with pre-existing resected astrocytoma; and grade 3 alkaline phosphatase elevated in patient with baseline fatty liver disease and baseline abnormal LFTs).

Pancreatitis

Seattle Genetics performed an internal qualitative review of all cases of acute pancreatitis received to date. As of June 30, 2013, Seattle Genetics has received reports of acute pancreatitis associated with brentuximab vedotin resulting in an incidence of 0.27% from clinical trials and compassionate use programs, and 0.07% from other patient exposures. The occurrence of acute pancreatitis contributed to a fatal outcome in 2 patient reports. Most of the cases of acute pancreatitis were reported within the first or second cycle of dosing. Some of the cases were confounded by other possible contributory factors, including concomitant administration of medications known to be associated with pancreatitis and possible alternate etiologies (including cholelithiasis and pancreatic lymphoma progression).

Re-challenge experiences with subsequent dose(s) after resolution of the acute pancreatitis were documented in 3 patients. Two of these patients did not experience recurrent acute pancreatitis on re-challenge. In the third patient, 2 re-challenge doses were administered without an elevation in pancreatic enzyme; however, following the third re-challenge dose, the patient experienced a recurrence of acute pancreatitis.

Based on this information, Seattle Genetics considers acute pancreatitis to be an important potential risk associated with brentuximab vedotin dosing, and will be updating the Investigator's Brochure accordingly.

Infusion reactions

Two cases of anaphylaxis were reported in phase 1 trials. There were no Grade 3 or 4 infusion-related reactions reported in the phase 2 trials, however, Grade 1 or 2 infusion-related reactions were reported for 19 patients (12%). The most common adverse reactions ($\geq 2\%$) associated with infusion-related reactions were chills (4%), nausea (3%), dyspnea (3%), pruritus (3%), pyrexia (2%), and cough (2%).

Serious adverse reactions

In the phase 2 trials, serious adverse reactions, regardless of causality, were reported in 31% of patients receiving Brentuximab vedotin. The most common serious adverse reactions experienced by patients with HL include peripheral motor neuropathy (4%), abdominal pain (3%), pulmonary embolism (2%), pneumonitis (2%), pneumothorax (2%), pyelonephritis (2%), and pyrexia (2%). The most common serious adverse reactions experienced by patients with sALCL were septic shock (3%), supraventricular arrhythmia (3%), pain in extremity (3%), and urinary tract infection (3%). Other important serious adverse reactions reported included one case each of PML, Stevens-Johnson syndrome and tumor lysis syndrome.

Dose modifications

Adverse reactions that led to dose delays in more than 5% of patients were neutropenia (14%) and peripheral sensory neuropathy (11%).

Discontinuations

Adverse reactions led to treatment discontinuation in 21% of patients. Adverse reactions that led to treatment discontinuation in 2 or more patients with HL or sALCL were peripheral sensory neuropathy (8%) and peripheral motor neuropathy (3%).

1.2.1.2 Mechanism of Action

Brentuximab vedotin (ADCETRIS[®]) is an antibody-drug conjugate (ADC). The antibody is a chimeric IgG1 directed against CD30. The small molecule, MMAE, is a microtubule disrupting agent. MMAE is covalently attached to the antibody via a linker. Nonclinical data suggest that the anticancer activity of Brentuximab vedotin is due to the binding of the ADC to CD30-expressing cells, followed by internalization of the ADC-CD30 complex, and the release of MMAE via proteolytic cleavage. Binding of MMAE to tubulin disrupts the microtubule network within the cell, subsequently inducing cell cycle arrest and apoptotic death of the cells.

1.2.1.3 Pharmacodynamics

The effect of brentuximab vedotin (1.8 mg/kg) on the QTc interval was evaluated in an open label, single-arm study in 46 evaluable patients with CD30-expressing hematologic malignancies. Administration of brentuximab vedotin did not prolong the mean QTc interval > 10 ms from baseline. Small increases in the mean QTc interval (< 10 ms) cannot be excluded because this study did not include a placebo arm and a positive control arm.

1.2.1.4 Pharmacokinetics

The pharmacokinetics of brentuximab vedotin were evaluated in phase I trials and in a population pharmacokinetic (PK) analysis of data from 314 patients. The pharmacokinetics of 3 analytes were determined: the ADC, MMAE, and total antibody. Total antibody had the greatest exposure and had a similar PK profile as the ADC. Hence, data on the PK of the ADC and MMAE have been summarized.

1.2.1.5 Absorption

Maximum concentrations of ADC were typically observed close to the end of infusion. A multiexponential decline in ADC serum concentrations was observed with a terminal half-life of approximately 4 to 6 days. Exposures were approximately dose proportional from 1.2 to 2.7 mg/kg. Steady-state of the ADC was achieved within 21 days with every 3-week dosing of brentuximab vedotin, consistent with the terminal half-life estimate. Minimal to no accumulation of ADC was observed with multiple doses at the every 3-week schedule. The time to maximum concentration for MMAE ranged from approximately 1 to 3 days. Similar to the ADC, steady-state of MMAE was achieved within 21 days with every 3 week dosing of brentuximab vedotin. MMAE exposures decreased with continued administration of brentuximab vedotin with approximately 50% to 80% of the exposure of the first dose being observed at subsequent doses.

1.2.1.6 Distribution

In vitro, the binding of MMAE to human plasma proteins ranged from 68-82%. MMAE is not likely to displace or to be displaced by highly protein-bound drugs. In vitro, MMAE was a substrate of P-gp and was not a potent inhibitor of P-gp.

In humans, the mean steady state volume of distribution was approximately 6-10 L for ADC.

